6.3.2 Software

All statistical analyses will be performed using Statistical Analysis Software (SAS[®]) Version 9.2 or later [1]. The PK analysis will be performed using Phoenix WinNonlin (version 6.3, or higher, Certara, Princeton, New Jersey) in accordance with PXL SOPs.

6.3.3 Missing Data

Missing dates and times in the AE data will be handled as described in Section 6.3.11.1. Concentrations that are BLQ in the PK data will be handled as described in Section 6.3.9.2.

There will be no imputations of other missing data. All subjects will be included into the safety analysis set as far as the data permit.

6.3.4 Baseline Definition

Baseline will be the last available non-missing value prior to IMP. Scheduled or unscheduled measurements can be used as the baseline value. Measurement specific baseline time points based on planned time points in the protocol are presented in Table 5.

Category	Measurement	Definition of Baseline
Safety	Vital signs	Pre-dose Day 1; if missing, Day -1; if missing, Screening
	Clinical laboratory	Day -1, if missing Screening
Immunogenicity	ADA	Pre-dose Day 1

ADA=Anti-drug antibody.

Statistical Analysis Plan

6.3.5 Interim Analysis

No interim analyses will be performed in this study.

6.3.6 **Protocol Deviations**

Protocol deviations are considered any deviation from the clinical study protocol relating to a subject, and include the following:

- Inclusion/exclusion criteria deviations
- Subjects who developed IP discontinuation criteria during the study but were not discontinued
- Dosing deviations (e.g., incorrect treatment (device) received, subject was not fasted as per the protocol requirements prior to and after dosing)
- Time window deviations for safety and/or PK assessments
- Subjects receiving prohibited concomitant medications
- Other procedural and study conduct deviations recorded by the clinical unit on a protocol deviation log

The criteria for the assessment and reporting of protocol deviations will be stipulated in a separate study specific protocol deviation specification (PDS) document. All protocol deviations will be discussed at the data review meeting (DRM) prior to database hard lock in order to define the analysis sets for the study. All disallowed medications will be reviewed before the DRM by the PK Scientist and Biostatistician, noted in the DRM Report and included in the DRM Minutes for any medications that lead to discontinuations.

Important deviations will be those which are considered to potentially impact upon the interpretation of the primary PK endpoint in the study. Only important protocol deviations will be listed and tabulated in the Clinical Study Report (CSR) [Appendix 16.2.2.1]. Subjects excluded from the PK analysis set will be listed [Appendix 16.2.3.1]. Data excluded from the PK analysis set will be listed in [Appendix 16.2.3.2] if applicable.

6.3.7 Demographic and Baseline Data

All demographic and baseline data will be presented using the Safety analysis set. All summary statistics for age (years) and height will be given as whole numbers. The weight and BMI will be presented to one decimal place. For categorical parameters percentages are presented with one decimal place.

Disposition

Subject disposition of study completion and withdrawal will be summarized by treatment (device) group and overall [Table 14.1.1]. Subject population disposition will be summarized overall [Table 14.1.2].

A listing of informed consent response [Appendix 16.2.1.2.1-16.2.1.2.2] and a randomization listing, to include body weight category and injection site will also be presented for each site (Germany and United Kingdom) separately [Appendix 16.2.1.3.1-16.2.1.3.2]. Subjects discontinuing from the study will be listed [Appendix 16.2.1.1], this will include duration of study and reason for discontinuation.

Demographic data

Demographic variables (Age, Sex, Race, Ethnicity, Height, Weight and BMI) will be listed by randomized subjects [Appendix 16.2.4.1]. Weight is measured at Screening at Day -1, height only at Screening, both will be listed [Appendix 16.2.9.4].

The summary statistics of weight, height and BMI will be based on the measurements at Day -1. If either weight or height is missing in a subject, the Screening measurement will be summarized.

Demographic characteristics (Age, Sex, Race and Ethnicity) will be summarized by treatment (device) and overall [Table 14.1.3]. The denominator for percentages will be the number of subjects in the Safety analysis set per treatment (device).

Subject characteristics (Height, Weight and BMI) will be summarized separately by treatment (device) and overall [Table 14.1.4].

Medical history

Medical history data will be listed by randomized subjects including visit, description of the disease/procedure, MedDRA SOC, MedDRA Preferred Term (PT), start date, and stop date (or ongoing if applicable) [Appendix 16.2.4.2].

Pregnancy test results (including FSH) will be listed [Appendix 16.2.8.11].

6.3.8 Prior and Concomitant Medication

Prior medications are those that started and stopped prior to the first dose of Investigational Medical Product (IMP); all medications taken after first dosing are considered as concomitant (including medications that started prior to dosing and continued after).

Prior and concomitant medication will be listed [Appendix 16.2.4.3] by randomized subjects and will include the following information: reported name, preferred term, the route of

Statistical Analysis Plan

administration, dose, frequency, start date/time, duration and indication. The duration will be calculated as:

Duration = end date/time – start date/time

The duration may be presented in hours or days in the listing depending on the applicability to the emerging data. For medications with partial or completely missing start date/times and/or end date/times, the duration will not be calculated. Medications with missing or partial start date/time and/or end date/time such that it is not possible to classify as prior or concomitant will be considered as concomitant in the listings.

6.3.9 Pharmacokinetic Concentrations and Variables

All tables and figures in this section will be based on the PK analysis set; all listings in this section will be based on the Safety analysis set unless otherwise specified.

6.3.9.1 Data presentation

Descriptive statistics and listings of concentration data and parameters

PK concentration data will be listed to the same number of significant figures as the data received from the bioanalytical laboratory. All descriptive statistics of PK concentration will be presented to 4 significant figures with the exception of the minimum and maximum which will be presented to 3 significant figures.

For PK parameters data, the listings will be presented according to the following rules:

- C_{max} will be presented to the same number of significant figures as received from the bioanalytical laboratory
- T_{max} will be presented as received in the data, usually to 2 decimal places
- AUC_{inf}, AUC_{last}, $t_{1/2}$, CL/F and V_z /F will be presented to 3 significant figures
- λ_z will be presented to 5 significant figures
- %AUC_{extra} will be presented to 2 decimal places

For PK parameters data the descriptive statistics of the PK parameters will be presented according to the following rules:

• C_{max} , AUC_{inf}, AUC_{last}, $t_{1/2}$, CL/F and V_z/F – all descriptive statistics will be presented to 4 significant figures with the exception of the minimum and maximum which will be presented to 3 significant figures

Statistical Analysis Plan

• T_{max} – all descriptive statistics will be presented as received in the data, usually to 2 decimal places

ADA status will be evaluated as a potential exclusion criterion for subject data included in the PK analysis. Serum concentration data associated with positive ADA status will be flagged in the PK concentration listings and may be excluded from the NCA, summary statistics and/or mean profiles, as determined based on emerging data and the formal DRM.

A listing of PK blood sample collection times, as well as derived sampling time deviations will be provided [Appendix 16.2.5.1], based on the safety analysis set. A listing of serum concentrations, based on nominal times only, will be presented [Appendix 16.2.6.1], based on the PK analysis set.

Serum concentrations and PK parameters will be summarized separately by treatment (device) only [Table 14.2.1.1] and by treatment (device), weight category [Table 14.2.1.2], injection site [Table 14.2.1.3] and injection site and weight category [Table 14.2.1.4]. In addition to the standard descriptive statistics the following will be presented: geometric mean, geometric CV% and geometric mean +/-SD. For T_{max} , only median, min, max and 95% CI will be presented.

All PK parameters will be listed [Appendix 16.2.6.2] (based on the PK analysis set) by treatment (device) and subject, and summarized by treatment (device) [Table 14.2.2.1].

The geometric mean is calculated as the exponential of the arithmetic mean calculated using log-transformed data.

The CV% is calculated as $100 \cdot \sqrt{\exp(s^2) - 1}$ where *s* is the SD of the log-transformed data.

Figures of concentration data

Combined individual serum concentration versus actual times will be plotted in linear and semi logarithmic scale shown on one page [Figure 14.2.1]. Separate plot panels will be presented for each treatment (device) by weight category and injection site.

Geometric mean serum concentration $(\pm SD)$ versus nominal sampling time will be plotted in linear and semi logarithmic scale (no SD presented for the semi logarithmic scale) with both scales on one page [Figure 14.2.2]. Separate plot panels will be presented for each treatment (device) by weight category and injection site.

For mean plots, BLQ values will be handled as described for the summary tabulations Section 6.3.9.2. For individual plots serum concentrations which are BLQ prior to the first quantifiable concentration will be set to a value of zero (linear plots only). After the first quantifiable concentration, any BLQ serum concentrations will be regarded as missing.

Statistical Analysis Plan

Likewise, concentrations Not Determined (ND) and Not Applicable (NA) will be set to missing.

Figures of PK parameters

Box plots of AUC_{inf}, AUC_{last}, C_{max} and $t_{1/2}$ will be provided by body weight group, separately for each parameter and with results from both devices displayed on the same plot side by side. A box plot will be superimposed on individual PK parameter values for each weight group. The top whisker will extend to the maximum value and the bottom whisker will extend to the minimum value; the middle bar will represent the median value; the mean value will also be displayed on the figures [Figure 14.2.3].

Results from the secondary analysis in Section 6.3.9.3 will be plotted: the geometric mean ratios of abdomen/arm, thigh/arm and thigh/abdomen and corresponding 90% CIs from the statistical pair-wise comparisons for AUC_{inf} , AUC_{last} and C_{max} will be presented in a forest plot for each treatment (device) [Figure 14.2.4].

All plots will be based on the PK analysis set.

6.3.9.2 Handling of Values Below the Limit of Quantification (BLQ) in Concentration Summaries and Listings

Serum concentrations that are BLQ or if there are missing values (e.g., no result [NR]) will be handled as follows:

- Where there is NR, these will be set to missing.
- At a time point where less than or equal to 50% of the values are BLQ, all BLQ values will be set to the LLOQ, and all descriptive statistics will be calculated.
- At a time point where more than half of the values are BLQ, the mean, SD, geometric mean and CV% will be set to Not Determined. The maximum value will be reported from the individual data, and the minimum and median will be set to BLQ
- If all values are BLQ at a time point, no descriptive statistics will be calculated for that time point. Not Applicable (NA) will be written in the field for standard deviation and CV% and BLQ will be written in fields for mean, geometric mean, minimum, median and maximum.
- The number of BLQ values (n below LLOQ) will be reported for each time point.

Statistical Analysis Plan

Three observations > LLOQ are required as a minimum for a serum concentration to be summarized. Two values are presented as a minimum and maximum with the other summary statistics as Not Calculated (NC).

Data from subjects excluded from the PK analysis set will be included in the data listings, but not in the descriptive statistics or in the inferential statistics.

6.3.9.3 Statistical Analysis of Pharmacokinetic Data

Primary PK analysis

The primary objective is to compare AUC_{inf}, AUC_{last} and C_{max} between APFS and AI devices following single SC administration of benralizumab. The analysis of variance (ANOVA) model will be employed on the log-transformed AUC_{inf}, AUC_{last} and C_{max}, separately, with fixed effects of treatment (device), body weight group and injection site in order to provide a descriptive comparison of the PK exposure between the 2 devices.

The estimated treatment (device) differences and the 90% CI (2-sided) on the log scale will be back-transformed to obtain the geometric mean ratios of AI to APFS and its corresponding 90% CI. The tables will also include the geometric least square means with 95% CI [Table 14.2.3.1]. Supporting statistical output for the analysis of PK parameters documented in Appendix 16.1.9.2.1.

The following SAS code will be applied, with AI sorted before APFS:

proc mixed data = <data>;

class <treatment_device> <weight category> <injection site>;

model <log_var> = <treatment_device> <weight category> <injection site>;

lsmeans <treatment_device> / cl alpha = 0.05;

```
estimate "AI versus APFS" <treatment_device> 1 -1 / cl alpha = 0.10;
```

run;

quit;

Secondary PK analysis

For T_{max} , a nonparametric analysis may be performed, based on evaluation during the blind data review.

To evaluate the PK of benralizumab administered to various anatomical injection sites and weight category, the PK parameters will be summarized by treatment (device) and injection sites [Table 14.2.2.3], and body weight categories [Table 14.2.2.2].

Furthermore, the ANOVA model of the primary analysis with the addition of the interaction term treatment (device)-by-injection site will be presented [Table 14.2.3.2]. The estimated differences of pairwise comparison between injection site within each treatment (device) and the corresponding 90% CI (2-sided) on the log scale will be back-transformed to obtain the geometric mean ratios of abdomen/arm, thigh/arm and thigh/abdomen and their corresponding 90% CIs.

Supporting statistical output for the analysis of PK parameters documented in Appendix 16.1.9.2.2.

The following SAS code will be applied:

proc mixed data = <data>;

class <treatment_device> <weight category> <injection site>;

model <log_var> = <treatment_device> <weight category> <injection site>
 <treatment_device> * <injection site>;

estimate "estimate details" <treatment_device> <injection site>

```
<treatment_device> * <injection site> specify 1s and 0s as applicable / cl alpha = 0.10;
```

run;

quit;

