### **8.9.2. Procedures for Randomization**

Upon completion of the randomization requirements specifications form, the randomization will be produced by PAREXEL according to the AZRand process.

A total of 180 subjects will be randomized. Subjects will be stratified by body weight category (55 to 69.9 kg/70 to 84.9 kg/85 to 100 kg). Within each of the 3 weight groups, subjects will be randomized 1:1:1:1:1:1 to one of the 6 combinations of treatment (APFS or AI) with injection site (upper arm, abdomen or thigh). As a result, 10 subjects will be allocated to each of the 18 randomization combinations for 2 device groups (Table 1). Randomization list will be prepared for each study site separately. Randomization number will be assigned to subjects sequentially within each weight category at each site. To keep the balance, each site must ensure they randomize subjects in complete blocks.

Once a randomization number has been allocated to a subject, it should not be assigned to another subject.

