### 11.9.4. Statistical Analysis of Pharmacokinetic Data

#### 11.9.4.1. Primary PK Analysis Method

The study primary objective is to compare AUC and  $C_{max}$  between APFS and AI devices following a single SC administration of benralizumab.

The analysis of variance (ANOVA) model will be employed on the log-transformed  $C_{max}$  and AUC separately, with fixed effects of treatment (device), body weight group and injection site in order to provide a descriptive comparison of the PK exposure between the 2 devices. The estimated treatment (device) differences and the 90% CI (2-sided) on the log scale will be back-transformed to obtain the geometric mean ratios of AI to APFS and its corresponding 90% CI.

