4. STATISTICAL BASIS FOR SAMPLE SIZE

While this study is not a formal bioequivalence study, a total of 162 subjects (81 subjects per group) are required for this study to achieve with 80% power and a 90% two-sided confidence interval (CI) for geometric mean ratios of area under the concentration-time curve (AUC) and maximum observed concentration (C_{max}) being within a limit of 0.8 to 1.25 inclusive. The calculation is based on two one-sided tests (TOST) at 5% alpha level under an assumption of maximum 50% coefficient of variation (CV) PK variability for primary endpoints of benralizumab AUC and C_{max} . Assuming 10% dropout rate, approximately 180 subjects will be enrolled to provide adequate numbers of subjects to assess the primary and secondary objectives of the study.

5. **RANDOMIZATION**

A total of 180 subjects will be randomized. Subjects will be stratified by body weight category (55.0-69.9 kg/70.0-84.9 kg/85.0-100.0 kg). Within each of the 3 weight groups, subjects will be randomized 1:1:1:1:11 to one of the 6 combinations of treatment (APFS or AI) with injection site (upper arm, abdomen or thigh). As a result, 10 subjects will be allocated to each of the 18 randomization combinations for 2 device groups (Table 1). Randomization lists will be prepared for each study site separately. Randomization numbers will be assigned to subjects sequentially within each weight category at each site. To keep the balance, each site must ensure they randomize subjects in complete blocks.

Once a randomization number has been allocated to a subject, it should not be assigned to another subject.

Day -1 body weight assessment will be used to categorize the body weight groups.

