6.3 Statistical Analysis Methods

6.3.1 Listings and Descriptive Statistics

All listings will include stratification factors (weight group and injection site). All summary tables will be presented by treatment (device), unless stated otherwise.

Demographic (Age, Sex, Race and Ethnicity) and baseline characteristics data will be summarized separately by treatment (device) and overall.

Pharmacokinetic data will be summarized separately by treatment (device) only and by treatment (device), body weight and injection site.

Adverse Events will be listed for each subject and summarized by System Organ Class and Preferred Term assigned to the event by Medical Dictionary for Regulatory Activities (MedDRA) Version 19.1.

Medical and surgical history will listed for each subject by System Organ Class and Preferred Term assigned to the event or history by MedDRA.

Prior and concomitant medication will listed for each subject by preferred drug name and medication as reported coded to preferred drug name using the World Health Organization Drug Dictionary Enhanced Plus Herbal (September 2016).

Frequency counts (number of subjects [n] and percentages) will be made for each qualitative variable. Descriptive statistics (n, Mean, Standard Deviation [SD], Median, Minimum and Maximum) will be calculated for each quantitative variable (unless otherwise stated). Descriptive statistics will only be presented if $n \ge 3$. For PK data, geometric mean, geometric mean +/- SD and coefficient of variation (CV%) based on log-transformed data will be presented.

Unless otherwise stated rules for decimal places are as follows:

- n and N the population total are always given as whole numbers,
- Ratios 2 decimal places,
- All measured data will be listed with the same number of decimal places or significant figures (with same precision) as the original raw data, with the exception of data for which the original number of decimals exceeds four decimal places; in these cases the data will be presented to three significant figures,
- An extra digit of precision will be added (typically four significant digits in total) for reporting of the geometric least-squares (LS) means and bounds of all confidence intervals within inferential analyses,

• A maximum of three decimal places will apply to all summary statistics.

The following rules will apply to any repeated safety assessments occurring within the treatment period:

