6.3.12 Changes of analysis from protocol

• The only results to be captured in DataLabs for physical examination are abnormal results as described in the protocol amendment 1. Abnormal results at baseline will be included as part of Medical History and abnormal results post baseline will be included as AEs. As a result, physical examination will not be listed by body system for each subject and each time point.

7. **REFERENCES**

- 1. SAS[®] Version 9.2 or later (SAS Institute, Cary, North Carolina, United States of America).
- 2. Phoenix[®] WinNonlin[®] 6.3 (or higher) (Certara, L.P., Princeton, New Jersey, USA).

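### Centre stratifies the randomisation but is in neither PK ANOVA model; adding it costs 1 df and can only help the precision of the device ratio

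*SAP*

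**What the plan says.** Protocol 8.9.2 states: "Randomization list will be prepared for each study site separately". SAP Section 5 repeats this and adds: "Randomization numbers will be assigned to subjects sequentially within each weight category at each site". It continues: "To keep the balance, each site must ensure they randomize subjects in complete blocks". There are two centres (SAP Section 2), so the lists define 3 × 2 = 6 strata.

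The protocol's primary model (11.9.4.1) is an ANOVA "with fixed effects of treatment (device), body weight group and injection site in order to provide a descriptive comparison". SAP 6.3.9.3 likewise specifies an ANOVA "with fixed effects of treatment (device), body weight group and injection site", and its code has the same terms: "model <log_var> = <treatment_device> <weight category> <injection site>". The secondary model adds only the device-by-injection-site interaction. Centre is in no CLASS or MODEL statement.

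SAP 6.3.1 says: "All listings will include stratification factors (weight group and injection site". Injection site is part of the randomised assignment, yet it is named as a stratification factor. Centre, which does divide the lists, is not. Centre appears only where SAP 6.3.7 splits the consent and randomisation listings by country. SAP 6.3.12 does not mention it.

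**The concern.** The trial balances device within centre, but the analysis does not use that balance. The true variance of the device contrast contains no centre difference, whereas the residual used to build the CI does. The reported interval then tends to be too wide and to cover more than 90% of the time.

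The 90% CI of the device ratio is the result for the primary objective, so its width matters. Only precision is at stake. The estimate is not biased, and the analysis is not invalid.

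**Working it through.** **Inputs from the documents.** 162 evaluable subjects, 81 per device; TOST at 5%; limits 0.80 to 1.25; CV at most 50%; 10% dropout; 180 randomised (Protocol 11.4, SAP Section 4). Two centres.

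**Assumed, because the documents are silent.** True device ratio 1; ratio R of exposure between centres of 1.1, 1.2 or 1.3; 50:50 split between centres.

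**1. The plan's own sample size.** Log variance s² = ln(1 + 0.5²) = 0.2231, SD 0.4724. Exact TOST power for two groups requires 78 per group. Rounding up to 9 in each of the 9 cells per device gives 81, with power 82.3%. 162/0.9 = 180. The plan's figures are consistent.

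**2. Cost of the term.** Residual df = 162 − 1 − 1 − 2 − 2 = 156, and 155 with centre. The one-sided 5% t quantile rises from 1.65468 to 1.65474, or 0.004%. With no centre effect, power is 82.2% either way.

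**3. Width.** With centre fitted, the half-width at CV 50% is 1.65474 × √(2 × 0.2231/81) = 0.1228, a CI of 0.884 to 1.131 around 1. Without centre, the expected residual variance is s² + (162/156)a, where a = p(1 − p)(ln R)² and p is one centre's share. For R = 1.2: a = 0.25 × 0.0332 = 0.0083; (162/156) × 0.0083 = 0.0086; √(1 + 0.0086/0.2231) = 1.019, so the interval is 1.9% wider.

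**4. Coverage and power.** With balance within centre, the device estimate keeps variance 2s²/81. Only the residual is inflated: without centre it follows a noncentral chi-square (df 156, noncentrality 162a/s²), and with centre a central chi-square (df 155). TOST power is integrated over that residual.

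| Without centre | R = 1.1 | R = 1.2 | R = 1.3 |
|---|---|---|---|
| a | 0.0023 | 0.0083 | 0.0172 |
| Half-width increase, CV 50% | 0.5% | 1.9% | 3.9% |
| Half-width increase, CV 40% | 0.8% | 2.9% | 5.8% |
| Half-width increase, CV 30% | 1.4% | 4.9% | 9.9% |
| Coverage of nominal 90% CI, CV 50% | 90.2% | 90.6% | 91.3% |
| Coverage of nominal 90% CI, CV 30% | 90.5% | 91.5% | 92.9% |
| Power, CV 50% within centre (82.2% with centre) | 82.0% | 81.2% | 80.1% |

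With a 70:30 split, power at CV 50% is 82.0%, 81.4% and 80.4%. If 50% is read as the total CV, s² becomes 0.2231 − a; power is then 82.5%, 83.0% and 83.9% without centre, against 82.7%, 84.0% and 85.9% with it.

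**5. Random loss.** Losing 18 of 180 subjects at random disturbs the exact balance. In 40,000 simulated trials at within-centre CV 50%, the half-width increased by 0.5%, 1.9% and 3.9%. Power was 81.8%, 80.9% and 79.4% without centre, against 82.0%, 82.0% and 81.8% with it. In a separate set of 8,000 trials per scenario, the mean error of the log device ratio was at most 0.0013 under either model.

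**The case against.** The case for leaving the model alone is reasonable:

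- **No error is shown.** The study is described as not a formal bioequivalence study and the ANOVA as descriptive. This stands, and it is why the point is only a suggestion.
- **No centre effect is documented.** Both units belong to one contract organisation and share eligibility rules, a fixed dose and supervised dosing. Body weight, by contrast, is a known PK covariate. This also stands: the ratios above are assumptions, and at 1.1 the loss is 0.3 power points.
- **The largest width increases matter least.** At CV 30%, power exceeds 99% with or without centre. At CV 40% and R = 1.3 it is 94.6% against 95.7%. This is correct.
- **The wider interval is only an expectation.** In a single trial with little centre difference, the CI without centre can be narrower. The gain is limited to about 0.3%, from √(156/155) × 1.65474/1.65468.
- **The change is late.** The study is open-label, SAP Final 2.0 is dated 04 August 2017, and the protocol expected the last subject to complete in June 2017. However, the SAP's introduction allows amendments up to database lock, and this term follows from the randomisation rather than from any result.

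None of this gives a reason to leave out a factor by which the trial already randomises.

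**Conclusion.** The point holds as a low-priority improvement. Centre is a stratum by construction and is modelled nowhere. The device ratio remains unbiased, provided that device stays balanced within centre and that exclusions from the PK set do not depend on device and centre jointly.

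The loss is nil if the centres are alike and modest if they differ by 20% to 30%. With exact balance within centre, the stated 80% power is met in every scenario tabulated. With the planned 10% random loss, it falls just short at an assumed centre ratio of 1.3 (79.4% without centre, 81.8% with it). The omission is conservative throughout.

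**What to change.** Before database lock:

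1. Add centre as a fixed effect to the CLASS and MODEL statements of both PROC MIXED models in SAP 6.3.9.3.
2. Name centre among the stratification factors in SAP 6.3.1.
3. Record the departure from the model in Protocol 11.9.4.1 under SAP 6.3.12, giving the separate lists as the reason.

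The cost is one term in two models and 1 df (156 to 155 in the primary model and 154 to 153 in the secondary, with 162 subjects). After lock, the SAP requires an addendum instead.

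A separate, optional item: every planned injection-site ratio is estimated within device, although the secondary objective names no device. The primary model could also supply abdomen/arm, thigh/arm and thigh/abdomen ratios pooled over device, as a descriptive supplement beside the within-device ratios. At CV 50% and 162 subjects, the 90% CI around 1 is 0.808 to 1.237 within device (27 v 27) and 0.860 to 1.162 pooled (54 v 54). With all 180 subjects it is 0.817 to 1.223 and 0.867 to 1.153. Pooling assumes similar site effects for both devices, which the design can check only roughly. The supplement can be dropped without affecting the centre change.

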### **8.10. Blinding**

This is an open-label study.

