### 11.5. Protocol Deviations

Protocol deviations are considered any deviation from the clinical study protocol relating to a subject. All protocol deviations will be discussed at the data review meeting prior to database hard lock in order to define the analysis sets for the study and all important protocol deviations will be listed by subject.

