#### **11.9.4.2. Secondary PK Analysis Method**

For  $T_{max}$ , a nonparametric analysis may be performed. Secondary PK parameters will be summarized.

To evaluate the PK of benralizumab administered to various anatomical injection sites, the PK parameters will be summarized by injection sites, body weight ranges and treatment (device). Furthermore, a similar ANOVA model for primary analysis may be used to include the interaction of treatment (device)-by-injection site.

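### The SAP names a blind data review that neither document defines, and nothing requires the discretionary PK exclusions in this open-label trial to be decided without sight of device

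*SAP*

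**What the plan says.** **Blinding.** Protocol 8.10 consists of one statement: "This is an open-label study".

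**The blind review.** SAP 6.3.9.3, under the secondary PK analysis, makes a nonparametric analysis of Tmax optional, "based on evaluation during the blind data review". This is the only place where either document attaches blindness to a data review. The matching text in Protocol 11.9.4.2 says that "a nonparametric analysis may be performed", with no reference to a review.

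**The DRM.** SAP 6.3.6 states: "All protocol deviations will be discussed at the data review meeting (DRM) prior to database hard lock in order to define the analysis sets". Protocol 11.5 says the same: deviations are "discussed at the data review meeting prior to database hard lock in order to define the analysis sets for the study". Neither place calls the meeting blind.

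**PK exclusions.** SAP 6.2.3 admits a subject to the PK analysis set if the samples are assumed to be unaffected by factors such as protocol violations; disallowed medication and incomplete dosing are its examples. SAP 6.3.9.1 allows concentrations linked to positive ADA status to be left out of the NCA, the summary statistics or the mean profiles, "as determined based on emerging data and the formal DRM".

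**Tmax in any event.** SAP 6.3.9.1 provides a descriptive summary whatever the review decides: "only median, min, max and 95% CI will be presented".

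**The concern.** The word blind tells the reader that a protection is in place, yet the documents never set it up. They do not say what is hidden, who is kept unaware, who holds the codes, or which meeting is meant.

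For Tmax alone this would be a small matter. The decisions that carry weight are those taken at, or with the help of, the DRM: who enters the PK analysis set, and whether ADA-positive concentrations go into the NCA that produces AUC and Cmax. Both rest partly on judgement, and the second is expressly left to the data as they emerge. In a two-device comparison, a judgement made with device and concentration side by side can shift the AI/APFS ratio, even without intent. The study is not a formal bioequivalence study and calls its comparison descriptive. But it is sized on two one-sided tests with limits of 0.80 to 1.25, and its rationale (Protocol 5.2) is to show comparable exposure, so readers will set the 90% CI against those limits.

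**Working it through.** **1. Is device masked anywhere?** The relevant places, side by side:

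| Place | What it provides |
|---|---|
| Protocol 8.10 | Open-label; nothing further |
| SAP 6.1.3 | Device type is recorded at dosing |
| Protocol 8.9.2, 10.5, 11.9.2 | The same contract research organization produces the randomization, manages the data and runs the NCA; no separation of roles is described |
| SAP 6.3.6 | Wrong-device dosing is a listed deviation, and all deviations go to the DRM |
| SAP 6.3.9.1 | PK parameters are listed by device |
| SAP 6.3.9.3 | A blind data review, undefined, for the optional Tmax analysis |

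None of these requires DRM material to be stripped of device. None says that it will carry device either. The supportable finding is that masking is undefined and not required.

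**2. What limits the discretion?** PK-set exclusion needs a sample affected by something such as a protocol violation (SAP 6.2.3). ADA exclusion needs a positive result, fixed at a titer of 50 or above (SAP 6.1.5). Deviations are discussed before hard lock (SAP 6.3.6). Exclusions are listed with reasons (Protocol 11.6; SAP Appendices 16.2.3.1 and 16.2.3.2).

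**3. How far could exclusions move the ratio?** The plan gives no figure for this, so I use its planning values from SAP section 4: 81 per arm, maximum CV 50%, limits 0.80 to 1.25. These inputs are sound: exact TOST power at 81 per arm is 82.3% if the true ratio is 1 and 80.7% if it is 1.02 (the documents do not state the assumed ratio), and 162/0.90 = 180.

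- Log-scale SD: s = √ln(1 + 0.5²) = 0.4724.
- 90% CI half-width: 1.6546 × 0.4724 × √(2/81) = 0.1228, a factor of 1.131.
- The interval fits inside the limits if the observed ratio lies between 0.80 × 1.131 = 0.905 and 1.25/1.131 = 1.105, which is about 0.100 on the log scale either side of 1.
- Removing k values, each 2 SD from the arm mean on the same side, shifts that arm's log mean by 2ks/(81 − k).
  - k = 1: 2 × 0.4724/80 = 0.0118, about 1.2%.
  - k = 5: 10 × 0.4724/76 = 0.062, about 6%, or 62% of the 0.100 available.

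**4. How extreme is the five-subject case?** Among 81 normal values, 81 × 0.02275 = 1.8 are expected beyond 2 SD on a given side, and the chance of five or more is about 4%. The case therefore amounts to picking out the most extreme values on one side of one arm. If five were removed at random, the SD of the shift would be 0.4724 × √(1/76 − 1/81) = 0.013, so 95% of shifts would stay within about 2.6%.

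**5. Simulation of the same worst case.** This used 4,000 runs with true ratio 1, CV 50% and the lowest values removed from one arm of 81.

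| Removed | Expected ratio | 90% CI inside 0.80–1.25 |
|---|---|---|
| 0 | 1.00 | 83.2% |
| 2 | 1.03 | 81.5% |
| 4 | 1.05 | 75.9% |
| 8 | 1.09 | 57.6% |

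These rows are upper bounds on what selective exclusion could do, not forecasts.

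**The case against.** The strongest reply is that the SAP keeps the two reviews apart. Blindness is claimed once, for an optional analysis of a secondary parameter; the DRM, which handles exclusions, is never said to be blind. So no safeguard was promised for the exclusions and then withheld. That stands. A reader might infer that the blind review and the DRM are one meeting, which is plausible, but the SAP does not say so.

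A reader might also infer that the reviewers will see device and concentrations together. The documents do not establish this. Open-label dosing is compatible with a review of listings without device codes, and blind may mean exactly that. Deviation criteria also sit in a separate specification that is not among these documents.

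Third, the discretion is bounded and traceable (step 2), and the primary ANOVA and its parameters are fixed in SAP 6.3.9.3. That also stands. What remains open is whether a given violation is judged to have affected the samples, and whether a positive ADA result leads to exclusion at all.

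Finally, masking cannot be complete. The DRM must discuss wrong-device dosing, and adverse events record device malfunction (SAP 6.1.6.1). This limits the remedy but does not defeat it: those cases can be handled separately.

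**Conclusion.** The point holds as an undefined safeguard, not as evidence that the review will be unblinded. The SAP uses the word blind without giving it content, and discretionary exclusions that feed the primary AUC and Cmax ratio need not be decided without sight of device.

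The likely effect is small: about 1.2% of the ratio for one 2-SD exclusion. The figure of about 6% assumes five same-direction 2-SD removals from one arm, the plan's maximum CV of 50% and 81 per arm. It should be read only as a worst case.

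It would be too strong to say that the fate of Tmax turns on this review. Its median, range and 95% CI are reported regardless; only the optional nonparametric analysis is at stake. Deciding exclusions without device codes is a cheap improvement on the procedure as written.

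**What to change.** In SAP 6.3.6 and 6.3.9.1, state that:

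- the blind data review is the DRM;
- PK-set and ADA exclusions are decided on listings with the device code removed and with no by-device summaries;
- all exclusions are signed off before the device code is merged;
- wrong-device and device-malfunction cases are handled in a separate listing.

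Also report the primary AI/APFS ratio with and without the excluded data.

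If masking is not intended, delete the word blind from SAP 6.3.9.3 and fix the ADA and PK exclusion rules before concentrations are reviewed.

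For Tmax, state in advance whether the nonparametric analysis will be done. The choice of estimator can be left to the sponsor.

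The cost is a few SAP sentences, one masked set of listings, a second run of the primary model and a small data-handling step for the PK vendor. Masking of device-related deviations will remain incomplete.
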